## **5. Baseline comparisons of key characteristics**

The following baseline characteristics of patients on each of the five study arms (including the non-randomised MDR group) will be tabulated and compared for each analysis population: age, gender, race, region, site, smoking status, HIV status/CD4 count, cavitation (based on blinded, central assessment of the chest radiograph (refer to Central Chest X-ray Manual), initial bacterial load in sputum as indicated by baseline Time to Positivity (TTP) result from MGIT, resistance to first and second line antibiotics and whether or not the patient is taking efavirenz.

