## **7. Determination of statistical non-inferiority**

The first comparison to be tested will be the MPa200Z 6 month experimental regimen against the standard regimen. The second comparison to be tested will be the MPa200Z 4 month experimental regimen against the standard regimen. The third comparison to be tested will be the MPa100Z 4 month experimental regimen against the standard regimen. To preserve the type I error rate, the second comparison will only be tested if non-inferiority is demonstrated with the 6 month experimental regimen. Similarly the third hypothesis will only be tested if non-inferiority of the PA-824 200mg 4 month regimen has been demonstrated. This strategy means no adjustments are required for multiple comparisons.

Non-inferiority will be assessed using the upper bound of the two-sided 95% confidence interval for the difference between the proportion of participants who are classified as having an unfavourable status on the intervention and the control regimen.

If the upper bound of the two-sided 95% confidence limit for the difference, proportion with unfavourable status on intervention arm less the proportion with unfavourable outcome on the control arm, is less than 12% (the margin of non-inferiority) the intervention will be considered to be non-inferior to the control arm on that comparison.

The PP and MITT analyses will be considered primary. However, in order to declare an intervention to be non-inferior, consistent results should be obtained from the ITT analysis and from sensitivity and subgroup analyses, although not all of these will necessarily satisfy the strict definition of non-inferiority.

All primary efficacy analyses of the three main analysis populations will be adjusted for HIV status and cavitation, using a stratified analysis of the risk difference from each stratum using Cochran-Mantel-Haenszel weights.

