## **11. Sub-group analyses**

To assess consistency of outcome, the following sub-group analyses (with tests for interaction) of the primary endpoint on the per-protocol and MITT analysis populations will be performed according to: age; gender; race; region; smoking status; HIV status/CD4 count; cavitation (based on blinded, central assessment of the chest radiograph), initial bacterial load in sputum as indicated by baseline TTP result from MGIT; whether the patient is taking efavirenz or not during the treatment period.

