#### Details of sample size and issues relating to choice of delta, the non-inferiority margin

The following assumptions have been made in calculating the numbers of subjects needed for the primary endpoint analysis.

- The unfavorable rate in the control regimen will be 16%, consistent with the control arm unfavourable rate in a recent Phase 3 TB trial.
- An unassessable rate of 15%, consistent with the overall unassessable rate in a recent Phase 3 TB trial.
- An additional 8% excluded for isoniazid mono-resistance, consistent with the overall percentage observed in a recent Phase 3 TB trial.
- An acceptable non-inferiority margin (delta) is 12% (see below)
- The power to demonstrate non-inferiority is 90% and the significance is 2.5% (1-sided).

Under these assumptions we would require 255 subjects for each treatment arm, giving a total sample size of 1,020 DS-TB subjects. Although these are considered to be reasonable assumptions based on recent data, in order to allow for the possibility of higher unfavorable and/or unassessable rates, or somewhat greater than 8% of subjects with INH mono-resistance, 300 DS-TB subjects will be recruited to each randomized arm giving a total of 1,200 subjects with DS-TB. Note that the primary analysis of the DS-TB subjects will exclude the subjects with isoniazid mono-resistance.

Examples of maximum observed effects which still meet the 12% margin for non-inferiority are given in Table A1 below for varying levels of the number N assessable and the proportion unfavourable in the control arm. Scenarios with observed differences of 6% or more are considered highly unlikely given the sample size for STAND is based on an expected MITT control arm unfavorable rate of 16% based on a recently completed phase 3 efficacy trial.

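### The efavirenz-by-arm interaction test in Section 11 is run in all patients, so it cannot attribute a difference in treatment effect to efavirenz rather than to HIV status

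*SAP*

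**What the plan says.** SAP Section 11 plans "sub-group analyses (with tests for interaction) of the primary endpoint on the per-protocol and MITT analysis populations", and gives the purpose as assessing consistency of outcome. The factors are listed one after another. One entry begins "HIV status/CD4 count; cavitation (based on blinded, central assessment of the chest radiograph"; the last is "whether the patient is taking efavirenz or not during the treatment period". Nothing restricts the efavirenz comparison to HIV-positive patients, crosses it with HIV status, or adds an HIV-by-arm term to its test. Section 5 likewise tabulates "whether or not the patient is taking efavirenz" with no HIV-positive denominator.

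Two statements in Section 7 bear on this. On adjustment: "All primary efficacy analyses of the three main analysis populations will be adjusted for HIV status and cavitation", by a stratified risk difference with Cochran-Mantel-Haenszel (CMH) weights. On the role of subgroups in declaring non-inferiority: "consistent results should be obtained from the ITT analysis and from sensitivity and subgroup analyses". The same sentence then allows that some of these analyses may fall short of the strict criterion.

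The SAP gives no HIV prevalence and no proportion on efavirenz.

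**The concern.** Listing efavirenz apart from HIV status suggests that the plan wants a separate answer about efavirenz. The planned split does not give one. Its user group lies wholly inside the HIV-positive population, while its non-user group contains all the HIV-negative patients. A treatment effect that varies with HIV status alone will therefore produce an efavirenz interaction. In the other direction, a true efavirenz effect feeds into the HIV contrast in proportion to the share of HIV-positive patients who take the drug.

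What is at stake is interpretation. Section 7 asks the team to look at subgroup consistency when it judges a regimen. Inconsistency labelled as efavirenz and inconsistency labelled as HIV point to different explanations, and the planned test cannot say which applies.

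**Working it through.** **Inputs from the SAP (Appendix 1).** The control rate ("The unfavorable rate in the control regimen will be 16"%), the unassessable rate ("An unassessable rate of 15"%), a further 8% excluded for isoniazid mono-resistance, a 12% margin, 90% power, one-sided 2.5% significance, and 300 recruited per arm.

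**The plan's own figure.** 2 × 0.16 × 0.84 × (1.960 + 1.282)² / 0.12² = 196.1. Dividing by 1 − 0.15 − 0.08 = 0.77 gives 254.7, so the stated 255 per arm reproduces and is not in dispute. The same deduction applied to 300 leaves 300 × 0.77 = 231 assessable per arm, which is used below.

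**Assumptions not in the SAP.** Efavirenz users are all HIV-positive, because it is an HIV drug. Let h be the HIV-positive share and s the share of those on efavirenz. The main range is h = 10-40% and s = 50-80%.

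**Carry-over.** The HIV-positive share of non-users is h(1 − s)/(1 − hs). If the treatment effect differs by D between HIV-positive and HIV-negative patients and efavirenz does nothing, the expected efavirenz interaction is D × (1 − h)/(1 − hs).

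| h | s | (1 − h)/(1 − hs) |
|---|---|---|
| 10% | 50% | 0.90/0.95 = 95% |
| 10% | 80% | 0.90/0.92 = 98% |
| 30% | 70% | 0.70/0.79 = 89% |
| 40% | 50% | 0.60/0.80 = 75% |
| 40% | 80% | 0.60/0.68 = 88% |

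Over the wider range h = 10-50% and s = 30-80% the carry-over is 59% to 98%. At h = 70% it is still 38% to 68%.

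**Rejection rates.** 20,000 simulated trials with 231 per arm, control risk 16%, h = 30%, s = 70%, no efavirenz effect, and a two-sided 5% Wald test of the difference between subgroup risk differences:

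| Regimen worse in HIV-positive patients by | Mean false efavirenz interaction, planned split | Planned test rejects | Within HIV-positive only, rejects |
|---|---|---|---|
| 0 points | 0 | about 5% | about 5% |
| 10 points | about 9 points | 17% | about 6% |
| 20 points | about 18 points | 47% | about 6% |

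Within HIV-positive patients the mean false interaction is about 0.

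**Does Section 7's stratification help?** No, even if it is carried over to Section 11. Users fall in a single HIV stratum. Among non-users, CMH weighting averages the HIV-positive and HIV-negative risk differences roughly in proportion to their numbers, so the mixture remains. With a 15-point HIV difference at h = 30% and s = 50%, the false interaction is 12.3 points and the rejection rate 22%, with or without the adjustment.

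**Precision of the alternative.** At h = 30% and s = 70% there are per arm 231 × 0.21 ≈ 49 users, 231 × 0.09 ≈ 21 HIV-positive non-users, and 231 − 49 = 182 non-users in all. With 16% unfavourable throughout:

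- Planned split: 1.96 × √[2 × 0.16 × 0.84 × (1/49 + 1/182)] = 16.4 points.
- HIV-positive only: 1.96 × √[2 × 0.16 × 0.84 × (1/49 + 1/21)] = 26.5 points.

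At h = 10% and s = 70% the restricted comparison is about 16 versus 7 per arm, with a half-width of about 46 points. Over the main range the standard error grows 1.3- to 2.1-fold.

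**The case against.** The strongest reply is that the analysis does its stated job. Section 11 aims to assess consistency, not to explain inconsistency. The 17% and 47% rejection rates arise only when the regimen really does perform worse in HIV-positive patients, so a flag of inconsistency is then correct. With no HIV-by-arm interaction, this source adds no bias. The HIV subgroup is reported beside it, and other listed factors may overlap too, such as cavitation and bacterial load. Most of this stands. It confines the problem to how a supportive result is labelled. It does not remove the problem, because a separate efavirenz test with its own p-value invites a conclusion about efavirenz.

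Three stronger readings are tempting and not supported:

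- A reader might infer that non-users are mostly HIV-negative. The SAP does not say so. It holds whenever h < 1/(2 − s), hence always below 50% HIV-positive, but the point needs only that some non-users are HIV-negative.
- A reader might infer that neither subgroup result can be interpreted. The estimate in users is still the effect in users, and the estimate in HIV-positive patients is still the effect in those patients as treated. Only the attribution of the contrast is ambiguous, and that is a limit of the planned test, not of the data.
- A reader might infer that this test could block a finding of non-inferiority. Section 7 sets the criterion on the 95% confidence limit against 12%, with PP and MITT primary. It asks for consistency without requiring every supportive analysis to meet the margin.

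The objection that the remedy is imprecise also stands, and the fix must say so.

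**Conclusion.** The point holds in limited form. As written, the efavirenz interaction test mixes an efavirenz effect with an HIV effect, and Section 7's stratification does not separate them. If the treatment effect differs by HIV status, an estimated 75% to 98% of the difference would appear under the efavirenz label, given 10-40% HIV-positive and 50-80% of those on efavirenz. Those ranges are assumptions, and the share falls as HIV prevalence rises. No effect on the primary non-inferiority conclusion is shown. The weight is that of a worthwhile correction to a supportive analysis.

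**What to change.** In Section 11, base the efavirenz interaction test and its interpretation on HIV-positive patients only, efavirenz yes versus no. Alternatively, fit HIV-by-arm and efavirenz-by-arm terms together; because no HIV-negative patient takes efavirenz, this targets the same contrast with the same imprecision. Keep HIV status as its own subgroup, and show the all-patient efavirenz split as descriptive, without a test.

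Add a sentence that the contrast within HIV-positive patients has low precision and that a non-significant result is not evidence of no efavirenz effect.

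The change is to SAP wording only and needs no new data. The price is the wider interval shown above, which at low HIV prevalence may leave the comparison close to uninformative.

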**12. Reasons for treatment failure as determined by the local PI**

Reason(s) that led the site investigator to conclude that an individual patient failed treatment or relapsed will be classified as a) bacteriology alone, b) clinical deterioration alone, c) radiological deterioration alone, d) bacteriology plus clinical deterioration, e) bacteriology plus radiological deterioration, f) clinical deterioration plus radiological deterioration, or g) bacteriology plus clinical deterioration plus radiological deterioration. These classifications will be tabulated and compared by treatment arm.

### 13. Appendix 1

#### Details of sample size and issues relating to choice of delta, the non-inferiority margin

The following assumptions have been made in calculating the numbers of subjects needed for the primary endpoint analysis.

- The unfavorable rate in the control regimen will be 16%, consistent with the control arm unfavourable rate in a recent Phase 3 TB trial.
- An unassessable rate of 15%, consistent with the overall unassessable rate in a recent Phase 3 TB trial.
- An additional 8% excluded for isoniazid mono-resistance, consistent with the overall percentage observed in a recent Phase 3 TB trial.
- An acceptable non-inferiority margin (delta) is 12% (see below)
- The power to demonstrate non-inferiority is 90% and the significance is 2.5% (1-sided).

Under these assumptions we would require 255 subjects for each treatment arm, giving a total sample size of 1,020 DS-TB subjects. Although these are considered to be reasonable assumptions based on recent data, in order to allow for the possibility of higher unfavorable and/or unassessable rates, or somewhat greater than 8% of subjects with INH mono-resistance, 300 DS-TB subjects will be recruited to each randomized arm giving a total of 1,200 subjects with DS-TB. Note that the primary analysis of the DS-TB subjects will exclude the subjects with isoniazid mono-resistance.

Examples of maximum observed effects which still meet the 12% margin for non-inferiority are given in Table A1 below for varying levels of the number N assessable and the proportion unfavourable in the control arm. Scenarios with observed differences of 6% or more are considered highly unlikely given the sample size for STAND is based on an expected MITT control arm unfavorable rate of 16% based on a recently completed phase 3 efficacy trial.

**Table A1. Scenarios demonstrating statistically non-inferior results**

Values are the maximum % difference between the intervention unfavourable rate minus the control, which if observed would be compatible with a 12% margin

N assessable per group	5% unfavourable in control arm	10% unfavourable in control arm	15% unfavourable in control arm	20% unfavourable in control arm
150	5.3%	4.0%	3.3%	2.6%
200	6.0%	5.0%	4.0%	3.5%
250	6.8%	6.0%	4.8%	4.0%
